7.4 Storage and analysis of clinical samples

Histological samples from TARGET patients are NHS clinical samples and as such are stored in NHS pathology laboratories. They will be retrieved for staining and analysis at NBT laboratories and may be transferred off North Bristol NHS Trust premises to facilitate the undertaking of p16 FISH. A Material Transfer Agreement will be completed for any and all transfers of samples to and from external sites for storage and/or analysis. Following completion of sample analysis they will be returned to the relevant NHS pathology laboratories.

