	Objectives	Outcome Measures		
Primary	Identify patients for whom additional pathological testing would have yielded a definitive diagnosis on baseline biopsy, avoiding the need for further invasive tests	Identification of malignancy on biopsy (binary; diagnostic vs non-diagnostic) via: i) histopathological confirmation on standard testing or histopathological features of PM with demonstrated BAP1, p16 or MTAP deletion or iii) Multi-disciplinary Team (MDT) diagnosis		
Secondary	i) Investigate whether additional pathological testing would have shortened the overall time to diagnosis and ii) Investigate whether additional testing would have reduced costs	i) Total number of biopsies required ii) Time to diagnosis iii) Stage at diagnosis iv) Number of MDT discussions required v) Biopsy-associated costs vi) Biopsy-related adverse events		

in whom additional testing would have provided a definitive diagnosis

iv. FUNDING AND SUPPORT IN KIND

FUNDER(S) (Names and contact details of ALL organisations providing funding and/or support in kind for this trial)	FINANCIAL AND NON FINANCIALSUPPORT GIVEN
Southmead Hospital Charity [name] [contact]	Research grant
NBT NHS Trust	Salaries for [name], [name], [name], [name]
NIHR	Salary for [name]
University of Bristol	Salary for [name]
University of West of England	Salary for [name]

v. ROLE OF TRIAL SPONSOR AND FUNDER

The Sponsor and Funders have no role or remit in the study design, conduct, data analysis and interpretation, manuscript writing or dissemination of results.

vi. ROLES AND RESPONSIBILITIES OF TRIAL MANAGEMENT COMMITEES/GROUPS & INDIVIDUALS

Study management group:

Responsible for oversight of the study. It will monitor trial progress, ensure all practical details of the trial are progressing well and feed back to the sponsor. The study management group will be chaired by the CI and will include all members of the named research team. It will meet 4 times during the study period.

Patient and Public Involvement group:

IRAS ID 329574

This will involve a specialist nurse and trial co-ordinator communicating details of the trial progress to a group of mesothelioma patients and carers as the study progresses.

Study delivery group:

This involves the people responsible for retrieving histological samples and performing and reporting the pathological tests. They will ensure accuracy and reproducibility of the tests, and updating the investigators on progress.

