3 OBJECTIVES AND OUTCOME MEASURES/ENDPOINTS

This research aims to answer the question: Could testing for BAP1, P16 FISH and MTAP IHC have removed the need for further invasive procedures in patients with suspected PM and an initial non-diagnostic biopsy?

We will address this question via the following objectives:

- Identify participants from the TARGET trial population (n=59)
- Extract historic biopsies (initial and repeat) from NHS pathology laboratories (n=129)
- Perform BAP1 and MTAP on all extracted biopsies. Where this fails to yield a diagnosis, perform additional p16 FISH.
- Identify patients for whom additional testing would have yielded a diagnosis, avoiding the need for further invasive tests (primary outcome).
- Investigate whether additional testing would have shortened the overall time to PM diagnosis (secondary outcome).
- Identify TARGET participants who ultimately received a clinico-radiological diagnosis, i.e. no tissue diagnosis was made, in whom additional testing would have provided a definitive diagnosis (sub-group analysis).

Primary and secondary outcomes, and outcome measures can be found in the study summary table.

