6 PARTICIPANT ELIGIBILITY CRITERIA

IRAS ID 329574

All patients recruited for the TARGET study will be included, provided they have sufficient stored biopsy material to undertake the required additional tests.

TARGET eligibility required all of the following to apply:

- Pleural thickening on CT suspicious for pleural malignancy
- Have had any form of pleural biopsy in the last 12 months (either by thoracoscopy or under radiological guidance) which was non-diagnostic for cancer
- Lung Cancer/mesothelioma MDT decision to perform further CT-guided biopsy to pursue a diagnosis

Participants were ineligible for TARGET if ANY of the following applied:

- Unsuitable for a CT guided biopsy (inability to co-operate, lie still for the duration of the biopsy, uncorrectable coagulopathy, inability to tolerate a pneumothorax, severe underlying lung disease [patients with an FEV1 < 35% assessed using simple spirometry])
- Unable to give written informed consent
- Pregnancy or lactation
- Age<18 years
 Pleural thickening not amenable to a radiologically guided biopsy
- Talc pleurodesis in the previous 6 months

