7.2 Consent

All patients in the study consented take part in the TARGET trial. They consented to have their anonymised data used in future research. Patients will have died by the time of this study, therefore we will not be able to obtain additional consent for use of non-anonymised data or biopsy samples. This study therefore requires CAG and ethical approval to access identifiable patient information while processing patient samples, so findings can be linked with clinical outcomes. TARGET consent form enclosed (Appendix 1)

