10 STATISTICS AND DATA ANALYSIS

The independent variable is the availability of BAP1, p16 FISH and MTAP testing (binary; available *vs* not available). The primary outcome is identification of malignancy on biopsy (binary; diagnostic *vs* non-diagnostic), with diagnosis defined as i) histopathological confirmation on standard testing or ii) histopathological features of PM with demonstrated BAP1, p16 or MTAP deletion or iii) Multi-disciplinary Team (MDT) diagnosis. It is assumed that confirmation of a malignant diagnosis stops the diagnostic pathway with no additional biopsies required. Any subsequent biopsies for these participants will not be included in the analysis, preventing double-counting. Secondary outcomes include total number of biopsies required, time to diagnosis, stage at diagnosis, number of MDT discussions, biopsy-associated costs, biopsy-related adverse events and survival. Potential confounding variables include age, sex, biopsy method and tumour histology and these will be adjusted for, when possible, in the analysis.

Outcome measures will be tabulated for standard and proposed pathways and compared using descriptive statistics (including the McNemar test). Univariable and multivariable logistic regression will look for an association between the availability of these tests and likelihood of a diagnostic biopsy. The relationship between secondary outcomes and availability of the tests will be evaluated using adjusted and unadjusted regression analyses and time to event analysis (cox proportional hazard model).

Sample Size:

Total number of patients: 59

Total histological samples for analysis: 129 (all participants had multiple biopsies)

REPLICA

IRAS ID 329574

Each participant will be assessed as a case (proposed pathway) and as an internal control (standard pathway) generating two groups of 59 = 118 records for inclusion in the study

Sample size is determined by the number recruited to the TARGET study which demonstrated diagnostic sensitivity (without these additional tests) of 30%. A sample size of 118 (59 in each arm) will allow detection of an increased diagnostic rate of 60% with 95% confidence intervals of +/- 8.8% (based on BAP1 loss prevalence of 60%).

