13.7 Access to data, data protection and patient confidentiality

All study documents will be stored securely in an access-restricted environment, accessible only to study staff and authorised personnel. Data will be collected and stored in accordance with the Data Protection Act 1998. Participants' personal data will be treated as strictly confidential. Anonymity of participants will be upheld by recording only participants' study number, initials and date of birth on key study documentation and analysis files. Only authorised study team members will have access to participants' personal data where this is necessary to link participants to their clinical records on clinical systems and for sample retrieval. No study information will be routinely shared with any external third parties. For the purposes of specific analyses, linked anonymised data may be shared. Only data required for each specific analysis will be shared. Any data being shared externally will be transferred securely electronically with password protection.

13.8 Financial and other competing interests for the chief investigator, PIs at each site and committee members for the overall trial management n/a

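### The protocol does not mask the readers of index biopsies to later biopsies, final MDT diagnosis or survival, so the proposed-pathway yield is at risk of upward review bias of unknown size

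*Protocol*

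**What the plan says.** **Who reads, and where.** Section 3 has the initial and repeat biopsies, 129 in all, retrieved for BAP1 and MTAP, with p16 FISH where these give no diagnosis. Section 7.4 states: "They will be retrieved for staining and analysis at NBT laboratories". It adds that samples "may be transferred off North Bristol NHS Trust premises to facilitate the undertaking of p16 FISH". Section vi (roles and responsibilities) gives one study delivery group the tasks of fetching the samples, running the tests and reporting them. Its only statement on the quality of reading is: "They will ensure accuracy and reproducibility of the tests, and updating the investigators on progress".

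**What identifying information is in use.** Section 7.2 seeks approval to "access identifiable patient information while processing patient samples, so findings can be linked with clinical outcomes". Section 13.7 limits personal data to authorised team members "where this is necessary to link participants to their clinical records on clinical systems and for sample retrieval". The same section has key documents and analysis files carry initials and date of birth alongside the study number.

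**What is already known.** Follow-up is complete (trial summary). Section 7.3 lists histological diagnosis, final MDT diagnosis and survival among the data to be extracted.

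**What is judged.** Section 10, criterion ii, counts a biopsy as diagnostic on "histopathological features of PM with demonstrated BAP1, p16 or MTAP deletion". Under section 6, each participant entered TARGET after a pleural biopsy "which was non-diagnostic for cancer".

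No section says whether the reader is masked to any of this.

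**The concern.** The primary comparison sets two readings of the same participant's tissue against each other. The standard index report was made before the repeat biopsy and before the final diagnosis. The new reading is made after both are on record. If the reader knows that a participant was later diagnosed with mesothelioma, equivocal morphology or partial loss of staining may more readily be called positive. The paired difference would then mix the value of the tests with the effect of hindsight, and the analysis could not separate the two.

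The section 3 sub-group is particularly exposed. These participants ended with a clinico-radiological diagnosis and no tissue diagnosis, so a clinical answer exists while the tissue was inconclusive.

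Sections 1 and 10 of the protocol's own logic make this matter: the aim is to change national guidelines, and the evidence for that is the gain in yield. Masking cannot be restored once slides have been read, so a later analysis plan cannot repair its absence.

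**Working it through.** **1. Does the text separate the reader from the outcome?**

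| Provision | What it does | Does it mask the reader? |
|---|---|---|
| Section vi, delivery group | Retrieval, testing and reporting sit in one group | No; it joins roles that masking would separate |
| 7.2 | Identifiable information in use during processing, for linkage | No; it also does not say that outcomes are shown |
| 7.4 | Staining and analysis at NBT; p16 FISH possibly off site | Silent |
| 11 | TARGET data extracted in anonymised form; laboratory data supplied by the laboratory team | Some separation of files; no rule for readers |
| 13.7 | Access limited to linkage and retrieval needs; files carry initials and date of birth | No; retrieval is a task of the reporting group, and these identifiers do not conceal identity |

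Outcome-aware reading is therefore left open. It is not prescribed.

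**2. In which direction can an error run?** By TARGET eligibility the index biopsy is non-diagnostic on standard testing for all 59 participants. At index level the standard-only cell of the McNemar table is therefore c = 0. Any upgrade, true or false, falls in the proposed-only cell b.

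**3. How much does each false upgrade count?** The protocol gives no figure for reading error. Its nearest figure is the precision of a 60% rate with 118 records: 1.96 × sqrt(0.6 × 0.4 / 118) = 8.84%, which reproduces the stated 8.8%. That is sampling error only and makes no allowance for biased reading.

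- One false upgrade: 1/59 = 1.7 points.
- Six: 6/59 = 10.2 points.
- Exact two-sided McNemar with c = 0: p = 2 × 0.5^b. For b = 5, p = 0.0625; for b = 6, p = 0.031.

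**4. What false-upgrade rates would matter?** Let f be the chance that a truly non-diagnostic index read is called diagnostic. The protocol gives no value, so f is an assumption, and reads are treated as independent. If the tests brought no true gain, the number of upgrades is Binomial(59, f):

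| f (assumed) | P(at least 6 upgrades) |
|---|---|
| 2% | 0.001 |
| 5% | 0.07 |
| 10% | 0.55 |
| 20% | 0.99 |

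With a true yield t, the observed yield is t + (1 − t) × f:

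- t = 60%: f of 5% to 20% gives 62% to 68%.
- t = 30%: f of 5% to 20% gives 33.5% to 44%.

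The effect ranges from negligible to serious across plausible-looking values of f, and nothing in the protocol narrows f.

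**The case against.** The strongest reply is that the protocol is silent and that silence is not an unmasked design. A reader might infer from section 7.2 that the pathologist will see the final diagnosis. The text does not support that: identity is not outcome, the stated purpose is linkage, and no section hands the reader the MDT diagnosis, the repeat result or survival. Section 13.7 restricts personal data, and section 11 keeps some distance between laboratory and TARGET data. This stands, and it limits the conclusion to a risk.

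A reader might also treat reading at one laboratory as the defect. It is not: central reading is no bias in itself, and p16 FISH may be done elsewhere.

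Next, criterion ii needs marker loss as well as morphology, so leniency on morphology alone cannot upgrade a case. Section 1 cites 100% specificity for BAP1 loss and for BAP1 combined with MTAP. This also stands in part: the marker requirement limits false upgrades. It does not exclude them, because loss of any one marker suffices as section 10 is worded, and the marker readings have no masking rule either.

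Finally, one might apply a shift of, say, 5% to 15% to all 59 reads and claim 5 to 15 points of bias. That is unsupported. The percentages are assumed, and truly positive reads cannot be moved upwards. At a true yield of 60%, only 59 × 0.4 = 23.6 reads are movable; 5% to 15% of these is 1.2 to 3.5 participants, or 2 to 6 points.

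The reply that masking detail may sit in a laboratory procedure does not settle the matter. The protocol refers to no such procedure for reading, and who sees what when the primary outcome is assigned is a design matter.

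**Conclusion.** The point holds as a risk. The protocol does not mask index readers to later biopsies, final diagnosis or survival, and the workflow it describes leaves outcome-aware reading open. At index level any resulting false upgrade can only favour the proposed pathway.

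The documents support "may bias" and not "biases", and the size cannot be derived from them. The reference figures (1.7 points per false upgrade; p = 0.031 at six with none the other way) rest on 59 evaluable participants and on the index-level comparison. The probabilities for a given f rest further on an assumed rate and independent reads. They show how few errors would matter; they do not estimate how many will occur.

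**What to change.** Amend section 7.4 to state that:

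- slides are labelled with a study code only, without initials or date of birth;
- a team member who does not read slides holds the linkage file;
- index and repeat slides are presented in mixed order;
- the reader records morphology and each marker result without access to the participant's other biopsies, MDT diagnosis or survival;
- the same masking applies to p16 FISH done off site;
- results are locked before they are linked to clinical data.

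Section 13.7 should be aligned, so that the identifiers it allows on study documents do not reach the reader. Identifiable information remains available for retrieval and linkage, as section 7.2 intends.

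The cost is coding, a linkage list and slightly slower slide handling. No extra reader, sample or test is needed.

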7.5 End of trial

The trial will be completed when all samples have been stained and reported, with all pathology reporting queries answered.

8 Safety reporting

There is no new patient contact, intervention or sampling as part of REPLICA. There is therefore no safety reporting required.

10 STATISTICS AND DATA ANALYSIS

The independent variable is the availability of BAP1, p16 FISH and MTAP testing (binary; available *vs* not available). The primary outcome is identification of malignancy on biopsy (binary; diagnostic *vs* non-diagnostic), with diagnosis defined as i) histopathological confirmation on standard testing or ii) histopathological features of PM with demonstrated BAP1, p16 or MTAP deletion or iii) Multi-disciplinary Team (MDT) diagnosis. It is assumed that confirmation of a malignant diagnosis stops the diagnostic pathway with no additional biopsies required. Any subsequent biopsies for these participants will not be included in the analysis, preventing double-counting. Secondary outcomes include total number of biopsies required, time to diagnosis, stage at diagnosis, number of MDT discussions, biopsy-associated costs, biopsy-related adverse events and survival. Potential confounding variables include age, sex, biopsy method and tumour histology and these will be adjusted for, when possible, in the analysis.

Outcome measures will be tabulated for standard and proposed pathways and compared using descriptive statistics (including the McNemar test). Univariable and multivariable logistic regression will look for an association between the availability of these tests and likelihood of a diagnostic biopsy. The relationship between secondary outcomes and availability of the tests will be evaluated using adjusted and unadjusted regression analyses and time to event analysis (cox proportional hazard model).

Sample Size:

Total number of patients: 59

Total histological samples for analysis: 129 (all participants had multiple biopsies)

REPLICA

IRAS ID 329574

Each participant will be assessed as a case (proposed pathway) and as an internal control (standard pathway) generating two groups of 59 = 118 records for inclusion in the study

Sample size is determined by the number recruited to the TARGET study which demonstrated diagnostic sensitivity (without these additional tests) of 30%. A sample size of 118 (59 in each arm) will allow detection of an increased diagnostic rate of 60% with 95% confidence intervals of +/- 8.8% (based on BAP1 loss prevalence of 60%).

On the assumption that the combination of BAP1 and MTAP will increase the diagnostic rate still higher, a sample size of 118 will allow detection of an increased diagnostic rate of 70% with 95% confidence intervals of +/- 8.2% and a diagnostic rate of 80% with 95% CI of 7.2%

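### The primary objective concerns the baseline biopsy, but section 10 defines and analyses the primary outcome over the whole diagnostic pathway, so the primary analysis does not measure how many repeat biopsies the new tests would have avoided

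*Protocol*

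**What the plan says.** **Objective.** The trial summary table (section iii) gives the primary objective as: "Identify patients for whom additional pathological testing would have yielded a definitive diagnosis on baseline biopsy, avoiding the need for further invasive tests". The Rationale (section 2) likewise speaks of re-testing the initial negative samples. The research question that opens section 3 concerns patients whose initial biopsy was non-diagnostic.

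**Outcome measure.** The same row of the summary table says only "Identification of malignancy on biopsy (binary; diagnostic vs non-diagnostic) via", followed by the routes to a diagnosis. Section 10 repeats this: "The primary outcome is identification of malignancy on biopsy (binary; diagnostic *vs* non-diagnostic". Neither names the biopsy that decides the result. The routes are standard histology, PM features with loss of a marker, or an MDT diagnosis.

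**Section 3.** The laboratory plan is "Perform BAP1 and MTAP on all extracted biopsies", covering initial and repeat samples (129). The primary outcome bullet reads "Identify patients for whom additional testing would have yielded a diagnosis, avoiding the need for further invasive tests (primary outcome". It omits the word baseline but keeps the condition that further tests are avoided.

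**Analysis.** Section 10 assumes that a malignant diagnosis ends the pathway and adds: "Any subsequent biopsies for these participants will not be included in the analysis, preventing double-counting". It compares the standard and proposed pathways with McNemar's test and with logistic regression on test availability. The planning figures are a 30% standard rate and a 60% rate with the new tests.

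**Eligibility.** Section 6 required every TARGET participant to have had a pleural biopsy that did not diagnose cancer.

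**The concern.** The study asks whether the extra stains, applied to the first biopsy, would have spared people a second procedure. Only the baseline biopsy can answer that for the first repeat procedure. If the binary outcome can be met at any point on the pathway, two different quantities share one name.

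A participant who stays negative at baseline and becomes diagnostic at repeat fails the stated objective but succeeds under section 10. Conversely, someone who would have been spared the repeat biopsy may add nothing to the paired test, because standard histology reached the diagnosis later and both pathways end as diagnostic. The headline percentage can therefore be too high as a measure of avoided biopsies, while the McNemar contrast is too small. If the choice between readings is left until the stains are read, the more favourable one can be picked.

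**Working it through.** **1. The plan's own figure.** The half-width is 1.96 × √(p(1 − p)/n) with n = 118.
- p = 0.6: 8.8 points (stated 8.8)
- p = 0.7: 8.3 points (stated 8.2)
- p = 0.8: 7.2 points (stated 7.2)

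The figures reproduce to within rounding. They treat the 118 records as one sample and do not depend on which biopsy decides the outcome.

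**2. Can section 10 be read as a baseline endpoint?** Three features say no.
- Later biopsies are dropped only after a malignant diagnosis, so repeat biopsies of undiagnosed participants stay in.
- Standard histology counts as a route to success. Section 6 required the qualifying biopsy to be non-diagnostic, so this route can essentially be met only on a repeat biopsy.
- The standard rate is 30%. At baseline it is 0/59 by eligibility, so 30% cannot be a baseline rate.

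**3. Illustration of the gap.** Assumptions, none stated in the Protocol for these biopsies:
- 60% marker yield at baseline. Section 10 gives 60% as an overall rate based on BAP1 loss.
- 30% standard yield at the repeat biopsy.
- Marker results agree fully between a person's biopsies.
- Baseline marker result and repeat standard result are independent.

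With n = 59 ("Total number of patients: 59"):
- Baseline endpoint: 0.60 × 59 = 35.4, about 35/59 (60%).
- Added at repeat by standard histology alone: 0.40 × 0.30 × 59 = 7.1.
- Pathway endpoint: (1 − 0.40 × 0.70) × 59 = 42.5, about 42/59 (72%).

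The 12-point gap contains no diagnosis made by the new tests. At an assumed 40% baseline yield the two rates are 40% and 1 − 0.60 × 0.70 = 58%.

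**4. The paired test under the same assumptions.**
- Marker-positive at baseline and diagnosed by standard testing at repeat: 0.60 × 0.30 × 59 = 10.6, about 11 people. They are diagnostic in both pathways, so concordant.
- Marker-positive at baseline and not diagnosed by standard testing at repeat: 0.60 × 0.70 × 59 = 24.8, about 25 people. These are the only discordant pairs.

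The pathway contrast is 72% − 30% = 42 points, although 60% had a baseline biopsy that became diagnostic.

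**5. What a result first seen at repeat can avoid.** Assume that the 129 samples are separate biopsies, one baseline and at least one repeat per person. Then 129 − 2 × 59 = 11, so at most 11 people had a third biopsy. For at least 59 − 11 = 48 people, a result first obtained at repeat avoids no later biopsy.

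**6. Precision of a baseline endpoint.** With one result per person (n = 59), the normal-approximation half-width is 12.5 points at 60%, 11.7 at 70% and 10.2 at 80%. The exact 95% interval for 35/59 is 45.7% to 71.9%. If about 10% of samples were unusable (n = 53), the half-width at 60% would be 13.2 points.

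**The case against.** **The documents mostly point one way.** The objective, the Rationale and the section 3 question all concern the initial biopsy. A reader might infer that the summary table fixes the baseline biopsy while section 3 accepts any biopsy. The documents do not support that. The table's own outcome measure already omits baseline, section 3 keeps the condition of avoiding further invasive tests, and the phrase any biopsy appears nowhere. The miscounting comes from section 10. This part of the objection stands.

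**Staining every sample proves nothing about the endpoint.** Repeat samples also serve the secondary outcomes and the subgroup with a clinico-radiological diagnosis. This stands too, and the point does not rest on it.

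**People diagnosed by standard histology at repeat do not bias McNemar's test.** They are diagnostic in both pathways and cancel. That is correct: they raise only the proposed-pathway percentage taken alone. But the same cancelling removes people whose repeat biopsy could have been avoided. The total number of biopsies required would capture them, but only as a secondary outcome.

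**The sizes are not the plan's.** A baseline yield of 60% is nowhere stated. The Background gives BAP1 loss in 40–60% of PM tumours, whereas TARGET enrolled people with suspected pleural malignancy. A reader might push the pathway rate to 84% (1 − 0.40²) by letting each biopsy convert independently at 60%, but the Protocol gives no basis for independence within a person. Nor is 48/59 a firm bound: 129 counts available samples, some people may have had more than one biopsy before enrolment, and invasive tests are a wider class than stored biopsies.

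**Conclusion.** The point holds in this form: the primary objective is about the baseline biopsy, while section 10, followed as written, analyses a whole-pathway endpoint. This conclusion rests on the text and on the 0/59 standard result at baseline, and needs no assumed yields.

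The sizes are illustrations only. On the stated assumptions the proposed-pathway rate is about 12 points above the baseline rate, and about 11 of 59 avoidable repeat biopsies become concordant pairs. That most results first obtained at repeat avoid no later biopsy depends on reading the 129 samples as separate biopsies with one baseline each.

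It is not a matter to leave to an analysis plan, because the Protocol's objective and its outcome definition disagree and one of them would have to be overridden.

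**What to change.** In the outcome measure of the summary table and in section 10, and for consistency in section 3, define the primary outcome as the proportion of participants with evaluable baseline tissue whose baseline biopsy becomes diagnostic with BAP1/MTAP and then p16 FISH. State that the standard-histology and MDT routes belong to the pathway outcomes.

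Because the standard result at baseline is 0 by design, report a single proportion with an exact 95% interval. McNemar's test would have discordance in one direction only, and logistic regression on test availability would separate completely, so neither should carry the primary result. Do not use 30% as the comparator for this outcome, and restate the expected precision on participants rather than on 118 records.

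Keep the whole-pathway comparison, with results first obtained on a repeat biopsy shown separately, as secondary. Count a biopsy as avoided only where a later one was performed.

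Staining does not change. The costs are a probably lower headline rate, a wider interval (about ±12.5 points instead of ±8.8 at 60%) and the loss of a two-arm test for the primary outcome.
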